### 3.2. Chemical Analysis

In this research, total fat, protein,  $\beta$ -glucan, total available carbohydrate, and total dietary fiber analyzes were performed chemically in the flour and bread samples. Chemical analyzes were performed in parallel and in duplicate. Data were reported on dry matter and average values of at least two analyzes were taken. The energy value (kcal) per test portion was calculated using the weight (g) of each test portion and the formula  $[(4 \times \text{protein}) + (9 \times \text{fat}) + (4 \times \text{available carbohydrate})]$  (19). All chemical analyzes were conducted in Erciyes University Veterinary Faculty Food Hygiene and Technology Laboratory.

All chemical analysis was performed as described above by taking a sample of several flours commonly available in Turkey. Among these flours, barley and oat flours with the highest  $\beta$ -glucan content were selected for baking bread as well as white flour and whole wheat flour having the most similar macronutrient content with barley and oat flours. A preliminary study was conducted to evaluate  $\beta$ -glucan content and bread baking tests were applied. For BB and OB, the content of  $\beta$ -glucan was targeted to be about 3 g in one serving. WB and WWB were used as reference and control foods, respectively. After the test breads were prepared, all the chemical analyzes described above were carried out again and the nutritional composition of the breads was found as in Table 1.

**Table 1.** Energy and macronutrient contents of test breads

	White bread	Whole-wheat bread	Barley bread	Oat bread
Portion size (g)	72	73	73	70
Energy (kcal)	150	147	154	133
Carbohydrate (g)	28.7	27.3	28.9	23.9
Protein (g)	5.0	5.7	4.9	4.7
Fat (g)	1.7	1.7	2.1	2.0
Dietary fiber (g)	2.2	6.8	6.9	9.0
$\beta$ -glucan (g)	1.2	1.4	3.1	3.2

### 3.3. Baking The Test Breads

For WB, WWB, BB, and OB, baking tests were performed using 100% white flour, whole wheat flour, barley flour, and oat flour, respectively. All breads have similar ingredients except the types of flour used. Dry yeast (2 g / 100 g), sugar (4 g / 100 g), salt (2 g / 100 g), and sunflower oil (4 g) in all breads were added (based on 100 g flour) (20). After resting for 30 minutes at room temperature (25 °C), the samples were fired in an electric oven at 180 °C for

30 minutes (21)(20). One serving size slices were wrapped in aluminum foil and packed in plastic bags to prevent drying and stored at -18 °C until use (22).

### 3.4. Test meals

The foods and nutritional composition of the test breakfast meals are as in Table 2.

**Table 2.** Nutritional composition of the component foods in test meals

Foods	Portion size (g)	Energy (kcal)	Carbohydrate (g)	Protein (g)	Fat (g)
Feta cheese	15	34.8	0.66	1.8	2.7
Cheddar cheese	24	79.2	0.48	5.28	6.24
Olive	24	57.1	0.30	0.32	4.79
Honey	20	64	16.6	0.06	-
Black tea	150 ml	-	-	-	-

### 3.5. Postprandial Appetite and Glucose Assessment

A visual analog scale (VAS) was used to assess appetite before breakfast and at 15, 30, 60, 90, 120, 150, and 180 minutes after breakfast (23). Furthermore, the separate VAS components such as hunger, fullness, desire to eat, and prospective food consumption were combined to produce an additional measure termed ‘composite appetite score’. This validated average appetite score was calculated for each time point using the following equation:  $[(\text{hunger} + \text{desire to eat} + \text{prospective food consumption} + (100 - \text{fullness}))]/4$  (24).

For the postprandial glucose assessment, blood glucose measurements were made using a finger-tip glucometer (Accu-Check, Roche Diagnostics) at 0, 15, 30, 45, 60, 90, and 120 minutes.

### 3.6. Ad libitum Lunch

At the end of three hours, the ad libitum lunch was served to the participants as a buffet-style, and the energy and macronutrient intakes in this meal were determined. All foods (meatballs, tuna, sauce pasta, yogurt, salad, white bread, apple, banana, yogurt drink, fruit juice, and water) were weighed using a calibrated kitchen scale with an accuracy of  $\pm 1\text{g}$  before being served. At lunch, the participants were asked to consume the foods they wanted and continue eating until they felt completely full. After the participants completed their consumption, the remaining amounts were reweighed and the difference with the initial amounts was accepted as the amount consumed. Energy and macronutrient values were calculated using The National Food Composition Database (TurKomp), and manufacturer labelling.

## 4. Statistical Analysis Plan

### 4.1. Sample size

A power-based sample size calculation based on previous research from Bo et al. (25) revealed that 16 participants were needed to provide 80% power to detect 5% difference between groups in primary outcomes. To allow discontinuation during the study, 20 participants (considering 25% losses) were recruited.

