### **3. Materials and methods**

#### *3.1. Participants and Study Design*

This study was planned as a multicenter, randomized, double-blind, and crossover. Approval was obtained from the Erciyes University Clinical Research Ethics Committee for the study (Decision No: 2018/259, Date: 09.05.2018). Twenty healthy adults (10 men, 10 women) between the ages of 19-35, with normal body weight (BMI 18.5-25 kg /m^2) were included in the study. Exclusion criteria were applying an energy-restricted diet in the last three months, having a change in body weight >5 kg in the last three months, having a chronic disease such as diabetes and hypertension, or using a drug that affects the metabolism, having fasting glucose >100 mg/dl, smoking, exercising heavily, having chewing/swallowing difficulties or sensitivity/allergies to any food to be used in the study, vegans, pregnant and lactating women, and skipping breakfast meals. Participants were selected from among Erciyes University students and staff in accordance with the inclusion criteria. Before the participants were included in the study, they were informed about the study in accordance with the Declaration of Helsinki, and volunteers were asked to read and sign the informed consent form.

The physical activity levels of the participants were evaluated simultaneously with dietary assessment by the International Physical Activity Questionnaire (IPAQ) short form at the beginning of the study and on each test day. Their dietary intakes were also assessed by the a-24-hour dietary recall using a photographic atlas of food portion sizes to quantify the data. Diet composition was analysed by the BeBiS Nutrition Information System software version 8.2. Furthermore, body weight and height of participants were obtained at the beginning of the study, and BMI was calculated. Waist and hip circumference were measured using a non-elastic tape with the participants standing, with the face directed towards, shoulders relaxed, and the tape was positioned at a level parallel to the floor. The eating behaviors of all participants were also evaluated using the Dutch Eating Behavior Questionnaire before starting the study. Since the total score obtained from this questionnaire >3.5 is considered as restrictive eating behavior (15), these individuals were not included in the study.

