### 4.2. Data analysis

Statistical analysis was performed using the SPSS Statistics (version 22.0) software. Data were expressed as the mean  $\pm$  SD unless otherwise indicated. Normality was assessed using the histogram and normal Q-Q plots, and also Shapiro-Wilk test. Postprandial appetite and glucose responses were quantified as incremental area under the curve (iAUC) calculated according to the trapezoidal rule. One-way analysis of variance (ANOVA) for repeated measures was applied to determine statistical differences between groups. For all statistical analyses, p values less than 0.05 were considered to have statistical significance.

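### Section 4.1 claims an allowance for 25% losses, but 20 recruits keep the required 16 completers only up to 20% losses

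*Combined protocol and SAP*

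**What the plan says.** Section 4.1 gives the requirement as "16 participants were needed to provide 80% power to detect 5% difference between groups in primary outcomes". It moves from 16 to the recruitment figure in one further sentence: "To allow discontinuation during the study, 20 participants (considering 25% losses) were recruited". Section 3.1 (Participants and Study Design) agrees on the number enrolled: "Twenty healthy adults (10 men, 10 women) between the ages of 19-35".

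The plan does not say what the 25% is a percentage of, and no other section defines it. Section 4.2 (Data analysis) plans a one-way repeated-measures ANOVA across the breads and does not say how participants with missing test days will be handled.

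**The concern.** Participants who discontinue come from those recruited, so an allowance for losses is normally a fraction of the recruited number. Read that way, the sentence promises that 16 participants remain after a quarter of the 20 have left. They do not. The result looks like a familiar slip: the required number was multiplied by one plus the loss rate when it should have been divided by one minus the loss rate.

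What is at stake is a stated property of the design. The loss allowance is the only reason given for recruiting 20 and not 16. In this crossover each participant is served all four breads, so 16 is most plausibly a number of completers. A reader of 4.1 would think the trial can lose five people and still meet its requirement, when it can lose only four.

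**Working it through.** **Inputs**

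- Required number: 16 (4.1)
- Stated loss rate: 25% (4.1)
- Number recruited: 20 (4.1, confirmed in 3.1)
- Target power: 80% (4.1)
- Significance level: 0.05 (4.2; sidedness not stated)

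**Step 1: reproduce the plan's figure.** Required number × (1 + loss rate) = 16 × 1.25 = 20. This matches exactly, so it is very probably how 20 was obtained.

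**Step 2: apply the stated loss rate to the recruits.** Recruited × (1 − loss rate) = 20 × 0.75 = 15. This is one below 16.

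**Step 3: find the loss rate that 20 recruits can absorb.** (20 − 16)/20 = 4/20 = 20%. Check: 20 × 0.80 = 16. The same four people are 4/16 = 25% of the required number, which is where the stated percentage comes from.

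**Step 4: find the recruitment needed for 25% losses.** Required number/(1 − loss rate) = 16/0.75 = 21.3, rounded up to 22. Check: 21 × 0.75 = 15.75, which is too few; 22 × 0.75 = 16.5, which is enough.

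| Reading | Recruits | Losses | Completers |
|---|---|---|---|
| As stated in 4.1 | 20 | 25% | 15 |
| What 20 recruits support | 20 | 20% | 16 |
| What 25% losses would need | 22 | 25% | 16.5 |

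**Step 5: power at 15 completers, for scale only.** Section 4.1 names no test, standard deviation or within-person correlation, so the 16 cannot be reproduced. Assume a two-sided paired t-test at 0.05 for one pair of breads, and assume that 16 is the smallest number reaching 80% power. Power is the probability that a noncentral t variable, with n − 1 degrees of freedom and noncentrality d_z × √n, exceeds the 97.5% point of the central t distribution. Here d_z is the mean paired difference divided by the standard deviation of the differences.

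| d_z | Power at n = 16 | Power at n = 15 |
|---|---|---|
| 0.749 (lower limit: 16 just reaches 80%) | 80.0% | 77.0% |
| 0.778 (upper limit: 15 would already reach 80%) | 82.8% | 80.0% |

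The upper limit is not itself attained, because 15 would then have been the required number. Power at 15 completers therefore lies from 77.0% to just under 80%.

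**The case against.** The strongest reply is that 4.1 does not state the base of the percentage. If 25% is an allowance added to the 16 needed, then 16 × 1.25 = 20 and the text is consistent. This explains how the figure arose, and it stands as a statement about arithmetic. It does not rescue the sentence, which is about discontinuation and uses the word losses; both refer to people already recruited. An ordinary reader will take it as 25% of 20, and on either reading the tolerable loss among recruits is four of 20.

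A second reply is that the point has almost no practical weight. That is largely right. The documents describe recruitment in the past tense, the shortfall is one completer, and it matters only if at least five participants are lost.

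A third is that the power range rests on a test the plan does not name for its sample size, while 4.2 names repeated-measures ANOVA. That is also right, and the range should be read only as an indication of scale. The finding rests on the whole-number arithmetic and does not depend on it.

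Finally, changing 25% to 20% could hide a shortfall if the investigators really expected a quarter of recruits to leave. That is a fair caution about the remedy and is taken up in the fix.

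**Conclusion.** The concern holds, as a minor point. Twenty recruits protect the requirement of 16 against losses of up to 20%, and the 25% stated in 4.1 would leave 15. The gap is one completer, or two recruits (22 against 20). This rests only on figures in 4.1 and 3.1 and on reading a loss rate as a share of those recruited. Under the assumptions given for the power calculation, the cost at 15 completers is at most about 3 percentage points against the 80% target. It is not evidence that the trial was underpowered, because actual losses are not given.

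**What to change.** Replace the second sentence of 4.1 with: *20 participants were recruited, allowing for 20% losses and leaving 16 completers.* This is true whichever base the authors had in mind. If they want to keep the 25%, they should name the base: four spare participants, equal to 25% of the 16 required and 20% of the 20 recruited. If 25% of recruits was the real planning expectation, 4.1 should say so and acknowledge that 22 would have been the matching number.

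The cost is one sentence and a slightly less favourable stated allowance. The correction calls for no further enrolment.

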### 4.2. Data analysis

Statistical analysis was performed using the SPSS Statistics (version 22.0) software. Data were expressed as the mean  $\pm$  SD unless otherwise indicated. Normality was assessed using the histogram and normal Q-Q plots, and also Shapiro-Wilk test. Postprandial appetite and glucose responses were quantified as incremental area under the curve (iAUC) calculated according to the trapezoidal rule. One-way analysis of variance (ANOVA) for repeated measures was applied to determine statistical differences between groups. For all statistical analyses, p values less than 0.05 were considered to have statistical significance.

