## 2. Objective

This study aimed to compare the postprandial effects of  $\beta$ -glucan on glycemia and appetite of breads derived from oats and barley, which are the best natural grain sources. In addition, the positive health effects of  $\beta$ -glucan were sought to be determined independent of total dietary fiber intake, using not only WB as the control food but also WWB, which has a dietary fiber content equal to that of breads containing  $\beta$ -glucan.

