Since individuals were asked to fast for at least 12 hours before consuming the test meals and the postprandial response was more pronounced in the morning, breakfast was chosen as the test meal. On the day before each test meal, the participants were asked to consume their standard dinner at 20:00 and not consume any food or beverage (except water) after dinner, and not to do any physical activity other than their daily routine activities. In addition, test meals were consumed in the follicular phase of the menstrual cycle in order to control the possible effects of the menstrual cycle on appetite for female participants. Similar to previous studies (16,17), days 3-10 after the onset of menses were accepted as the follicular phase.

Participants were served barley bread (BB), oat bread (OB), and wheat breads (WB and WWB) with a standard breakfast on four different days at least two days apart (18). Breads were prepared with similar amounts of energy, protein, fat, carbohydrate, and fiber (except WB). The test meal was served to the participants at 09:00 and they were asked to consume it within 15 minutes. During the test period, participants were not allowed to eat or drink anything other

than water. On the first day of testing, participants were able to consume as much water as they wanted and the amount consumed was recorded. On the other test days, they were asked to consume the amount of water recorded on the first test day. In addition, the participants were allowed to watch movies, read books, play games on electronic devices (computer, cell phone, etc.), and do other sedentary activities during the test days, but they were not allowed to sleep.

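### Adjusting appetite AUC for the same-day fasting score would usually be more precise than the unadjusted iAUC in section 4.2

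*Combined protocol and SAP*

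**What the plan says.** Section 4.2 (Data analysis) has one sentence for both response types: "Postprandial appetite and glucose responses were quantified as incremental area under the curve (iAUC) calculated according to the trapezoidal rule". The comparison follows: "One-way analysis of variance (ANOVA) for repeated measures was applied to determine statistical differences between groups". No baseline covariate is named. Neither this section nor any other says whether area below the fasting value is subtracted, set to zero or reported separately. The glycaemic index methodology paper is cited in section 3.1 for the spacing of test days, not for the area calculation.

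Section 3.5 says that a VAS "was used to assess appetite before breakfast and at 15, 30, 60, 90, 120, 150, and 180 minutes after breakfast". A fasting score therefore exists for every participant on every test day. In the same section, "hunger, fullness, desire to eat, and prospective food consumption were combined to produce an additional measure", with fullness entered as 100 minus the score. Section 3.1 describes the state before the meal: "Since individuals were asked to fast for at least 12 hours before consuming the test meals".

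Appetite is one of two stated aims; section 2 compares effects on "glycemia and appetite of breads derived from oats and barley". Section 4.1 says that "16 participants were needed to provide 80% power to detect 5% difference between groups in primary outcomes", but no section names those outcomes.

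**The concern.** Net iAUC is a change-from-baseline measure. The fasting VAS score is one noisy mark, and net area subtracts it across the whole curve. If a participant's post-meal scores follow that day's fasting score less than one for one, the subtraction adds noise to every bread comparison. With 16 to 20 participants, that can decide whether a moderate appetite effect is detected.

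A secondary matter is the unstated area rule. Glucose and fullness are expected to rise after breakfast. Hunger, desire to eat, prospective consumption and the composite are expected to fall. The documents do not say so, but it follows from a long fast followed by a meal. For these four measures, an area counted only above the fasting value would discard most of the response.

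**Working it through.** **Plan's own figures.** With 16 completers and four breads, the repeated-measures ANOVA has (16 − 1) × (4 − 1) = 45 error degrees of freedom. The sample size cannot be reproduced, because no SD is given. Back-solving a paired t-test (two-sided 0.05 assumed, since section 4.2 says only that "p values less than 0.05 were considered to have statistical significance") for 80% power at n = 16 gives a standardised difference of 0.749. That is an SD of paired differences of 5/0.749 = 6.7% of the mean. It says nothing about VAS precision and is not disputed here.

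**Step 1: what net area does.** At the VAS times in section 3.5 the trapezoid weights are 7.5 at fasting, 15 at 15 min, 22.5 at 30 min, 30 at each of 60, 90, 120 and 150 min, and 15 at 180 min. The post-meal weights sum to 172.5 and their squares to 4,556.25. Let x be the fasting score and M the weighted mean post-meal score.

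- Total AUC = 172.5 M + 7.5 x
- Net iAUC = total AUC − 180 x = 172.5 (M − x)

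Net area therefore analyses M − x, a slope of exactly 1 on x.

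**Step 2: variance in general.** Let β be the within-person slope of M on x. Per 172.5², and before the cost of estimating β:

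- Net: Var(M − x)
- Adjusted: Var(M) − β² Var(x)
- Net minus adjusted = (1 − β)² Var(x)

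The difference is never negative and is zero at β = 1.

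**Step 3: day shift fully shared.** Assume one day shift (variance S) common to all readings, plus independent reading noise (variance N). Then β = S/(S + N), and 4,556.25/172.5² = 0.153. Net variance is 1.153 N and adjusted variance is (β + 0.153) N, so the ratio is (β + 0.153)/1.153. It is 0.31, 0.57, 0.83 and 0.99 at slopes 0.2, 0.5, 0.8 and 0.985.

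**Step 4: day shift partly shared.** Let the fasting and post-meal shifts correlate at 0.5, with shift SD 8 (S = 64) and noise SD 4 (N = 16).

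- β = 0.5 × 64/80 = 0.40
- Net: 2 × 64 × 0.5 + 1.153 × 16 = 82.45
- Adjusted: 64 + 0.153 × 16 − 32²/80 = 53.65
- Ratio: 53.65/82.45 = 0.65

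The step 3 formula would give (0.40 + 0.153)/1.153 = 0.48, which overstates the gain.

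**Step 5: simulation on assumed inputs.** 20 participants, four breads, 2,000 runs per setting. Mean scores: 70 fasting, then 25, 25, 32, 40, 48, 55, 62. SDs: participant 8, fasting day-to-day 8, post-meal day 6, reading noise 4. One bread is 4 points lower after the meal.

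| Slope | SD of bread contrast, net | SD, adjusted | Change in SD | Power, net | Power, adjusted |
|---|---|---|---|---|---|
| 0 | 548 | 338 | −38% | 24% | 49% |
| 0.25 | 465 | 344 | −26% | 30% | 51% |
| 0.5 | 412 | 345 | −16% | 39% | 50% |
| 0.75 | 353 | 343 | −3% | 49% | 51% |
| 0.9 | 345 | 345 | 0% | 52% | 52% |
| 1.0 | 330 | 333 | +1% | 51% | 50% |

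**Step 6: net and total AUC after adjustment.** They differ only by 180 x. With x in the model, the bread estimates, standard errors and p-values are identical (largest difference about 1e-15). Only the slope on x changes, by exactly 1 on the time-averaged scale (0.6098 against −0.3902 in one mixed-model fit).

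**Step 7: the area rule.** For the assumed mean curve in step 5, total AUC is 7,642.5, net area is 7,642.5 − 180 × 70 = −4,957.5, and area above fasting is 0. In that simulation, 79% to 88% of test days had an above-fasting area of exactly zero.

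**The case against.** The strongest reply is that nothing in section 4.2 is wrong. Net area is the literal reading of a trapezoidal incremental area, and it is valid. Counting only area above fasting needs a further rule that the text does not contain. This stands: the main point concerns efficiency, and the missing area rule is missing detail.

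A second reply is that the agreement of net and total AUC answers a question the plan does not raise, since the plan says incremental. This also stands in part. Adjustment does not reconcile net with above-fasting area, which measures a different quantity, and other variants exist, such as area below baseline only. The case for adjustment rests on estimating the slope.

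A third reply is that the gains rest on invented curves and SDs. They do, and the slope-only formula holds only when the whole day shift is shared. The direction in step 2 does not depend on those values; the size does.

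A reader might infer that the satiety effect will be missed, or that false positives will rise because an analyst could keep the more favourable of two areas. The documents support neither. They do not say that above-fasting area was used, and they do not suggest choosing between results. Section 4.2 also calls for normality checks, which data made up mostly of zeros would visibly fail, although it states no fallback.

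**Conclusion.** The point holds as a better available analysis. For appetite, AUC adjusted for the same-day fasting score is usually more precise than net iAUC. It is never less precise apart from the small cost of estimating the slope.

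The size is conditional because the documents contain no VAS data. At slope 0.5 the variance ratio is 0.57 if the day shift is fully shared; at slope 0.40 with partly shared shifts it is 0.65; near slope 1 there is no gain. These figures illustrate the range and do not estimate this trial's power.

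The unstated area rule is a secondary gap. It matters for hunger, desire to eat, prospective consumption and the composite if area above fasting was used. Fullness and lunch intake do not share that direction problem. A reader might infer that the trial's main conclusion is at risk; that cannot be shown, because the primary outcomes are not named.

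**What to change.** For each VAS item and the composite, analyse AUC from 0 to 180 minutes in a linear model with participant (fixed), bread and the same-day fasting score, using one row per participant and visit. This replaces the one-way repeated-measures ANOVA, which cannot take a covariate that changes by visit. Either net or total AUC may be the response.

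State for each outcome, including glucose, how area below the fasting value is handled. If rebound above fasting is of interest, define it as a separate outcome.

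Section 4.2 is written in the past tense. If the analysis has already been run, report the area rule that was used and show the adjusted AUC beside it, labelled as a sensitivity analysis.

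Costs: one error degree of freedom (45 to 44 with 16 completers), an assumed linear relation with the fasting score, and about 1 point of power when the slope is near 1. The adjusted analysis does not target late rebound. No new data are needed.

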Overall, although studies have shown positive effects of  $\beta$ -glucan on appetite and postprandial glycemic response, it is not yet clear whether this positive effect is due to  $\beta$ -glucan or total dietary fiber intake. Also, since the majority of studies used products enriched with  $\beta$ -glucan, little is known about the possible effects of dietary sources with  $\beta$ -glucan in their natural form. In this study, the effects of breads derived from barley and oat, which are the best grain sources of  $\beta$ -glucan, on appetite and postprandial glycemia were examined and the possible effects of its natural dietary sources were determined. In addition, the effects of breads, which are a source of  $\beta$ -glucan, on appetite and postprandial glycemia were evaluated by comparing not only with white bread (WB) but also with whole wheat bread (WWB), unlike previous studies. In this way, it was aimed to determine whether the possible positive effects were due to  $\beta$ -glucan or total dietary fiber intake. The selection of bread, which is the most commonly consumed grain-based food in European countries, as the test food will make it easier to add possible positive results to healthy eating recommendations and to their applicability.

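### The only outcome test in section 4.2, a four-bread omnibus ANOVA, cannot separate β-glucan from total fibre, and the fibre-matched contrast (barley minus whole-wheat) is not named

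*Combined protocol and SAP*

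**What the plan says.** Section 1 (Background) gives the reason for the whole-wheat arm: "it was aimed to determine whether the possible positive effects were due to" β-glucan or to total fibre intake. Section 2 (Objective) repeats this, "using not only WB as the control food but also WWB, which has a dietary fiber content equal to that of breads containing" β-glucan. Section 3.1 likewise describes the breads other than white as similar in fibre. Section 3.2 assigns the roles: "WB and WWB were used as reference and control foods, respectively".

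The design is a crossover: "Participants were served barley bread (BB), oat bread (OB), and wheat breads (WB and WWB) with a standard breakfast on four different days".

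Section 4.2 gives one test for outcomes: "One-way analysis of variance (ANOVA) for repeated measures was applied to determine statistical differences between groups". It adds: "For all statistical analyses, p values less than 0.05 were considered to have statistical significance". The only other test mentioned is Shapiro-Wilk, for normality. There is no planned contrast, post-hoc procedure or multiplicity adjustment. Section 4.1 does not fill the gap. It claims "80% power to detect 5% difference between groups in primary outcomes" without saying which breads are compared or which outcomes are primary.

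**The concern.** With four breads, the null hypothesis of the repeated-measures ANOVA is that all four means are equal. Suppose fibre is all that matters and the fibre-rich breads behave alike: white bread differs, and whole-wheat, barley and oat do not. Rejecting the null is then correct, yet this is the explanation that the whole-wheat bread was added to rule out. The test and the question do not match, and a larger sample would not change that.

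What is at stake is the trial's distinguishing conclusion, an effect independent of total fibre. The design contains a comparison that bears on it, but the plan does not say that this comparison will be made, or how. If the pairs are left to be chosen later, oat versus whole-wheat could be used for the claim although those two breads are not matched on fibre.

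**Working it through.** **1. Which comparisons bear on the question (Table 1, section 3.2, per portion)**

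| Comparison | Fibre (g) | β-glucan (g) | Carbohydrate (g) |
|---|---|---|---|
| Barley vs whole-wheat | 6.9 vs 6.8 | 3.1 vs 1.4 | 28.9 vs 27.3 |
| Oat vs whole-wheat | 9.0 vs 6.8 | 3.2 vs 1.4 | 23.9 vs 27.3 |
| White vs whole-wheat | 2.2 vs 6.8 | 1.2 vs 1.4 | 28.7 vs 27.3 |

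Barley minus whole-wheat varies β-glucan at nearly equal fibre. White minus whole-wheat varies fibre at similar β-glucan. Oat minus whole-wheat varies both, with 2.2 g more fibre and 3.4 g less carbohydrate, so the equal or similar fibre described in sections 2 and 3.1 does not hold for oat bread.

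**2. The plan's own figure**

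The 16 completers of section 4.1 cannot be recomputed: no SD, within-person correlation, sidedness or pair of breads is given. Working backwards with a two-sided paired t test at 0.05 and 80% power, n = 16 corresponds to a paired difference of 0.749 SD of the difference. For a 5% difference, that implies an SD of 5/0.749 = 6.7%. In within-subject SD (σ, where the SD of a paired difference is σ√2), it is 0.749 × √2 = 1.06. Recruitment follows as 16 × 1.25 = 20.

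**3. Illustration of the mismatch**

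Assumptions: sphericity, two-sided tests, shifts δ in units of σ.

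- Omnibus: noncentral F on 3 and 3(n−1) df, noncentrality λ = n·Σ(μ − mean μ)²/σ². For n = 16 the critical value is F(3, 45) = 2.81.
- Only white bread shifted by 1: Σ = 0.75, λ = 16 × 0.75 = 12, power 80%.
- Barley and oat both shifted by 1: Σ = 1, λ = 16 × 1 = 16, power 91%.
- Barley minus whole-wheat: paired t on n−1 df, noncentrality δ√n/√2. With δ = 0 the rejection rate is 5%. With δ = 1 and n = 16 the noncentrality is 4/1.414 = 2.83 and power is 75%. With n = 20 it is 4.472/1.414 = 3.16 and power is 85%.

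| n = 16, shift (σ) | F, only white differs | F, barley and oat differ | Barley minus whole-wheat at 0.05, only white differs | Same contrast, barley and oat differ |
|---|---|---|---|---|
| 0.5 | 25% | 33% | 5% | 26% |
| 0.75 | 53% | 67% | 5% | 51% |
| 1.0 | 80% | 91% | 5% | 75% |

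At n = 20 and a shift of 1, F is significant in 90% and 97% of trials, and the barley contrast in 5% and 85%.

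**4. The same with the Table 1 grams**

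Let effects be linear in grams, with the largest between-bread difference set to 1.06σ and n = 16.

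- Fibre only (range 9.0 − 2.2 = 6.8 g): barley minus whole-wheat is 0.1/6.8 × 1.06 = 0.016σ, and oat minus whole-wheat is 2.2/6.8 × 1.06 = 0.34σ. F is significant in 70% of trials, the barley contrast in 5%, and the oat contrast in 15% at unadjusted 0.05.
- β-glucan only (range 3.2 − 1.2 = 2.0 g): barley minus whole-wheat is 1.7/2.0 × 1.06 = 0.90σ. F is significant in 90% of trials and the barley contrast in 66%.

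**5. Unadjusted follow-up of both whole-wheat contrasts (simulation, n = 16)**

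At least one of the two is significant in about 9% of trials if only white bread differs. If effects follow the fibre grams, the figure is about 18%. The excess comes from oat bread: its difference from whole-wheat is then real but due to fibre.

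**The case against.** The strongest reply is that pairwise follow-up after a repeated-measures ANOVA is routine, and that naming white bread as reference and whole-wheat as control shows that bread-to-bread comparisons were intended. Adjusted follow-up would also guard well against a wrong claim in the simplest case. If only white bread is shifted by 1σ at n = 16, six Bonferroni-adjusted pairs tested after a significant F falsely separate barley or oat from whole-wheat in about 1.7% of trials (simulated). The cost is power: barley is detected in about 45% when barley and oat are both shifted by 1σ.

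Part of this stands. A reader might infer that the sponsor will claim a β-glucan effect from a significant F alone. The documents do not support that: section 4.2 states no decision rule and is silent on follow-up. Nor is the 80% figure a false-positive rate, because the omnibus rejection is correct when white bread differs.

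What does not stand is that routine follow-up repairs the plan. No follow-up is stated, so the pairs and the adjustment remain open. Adjusting all pairs would also treat oat versus whole-wheat as evidence of the same kind as barley versus whole-wheat, and Table 1 shows that it is not.

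A reader might also take the barley contrast as proof that β-glucan is the cause. That goes too far, because the flours differ in other ways. The contrast can support an effect independent of total fibre.

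**Conclusion.** The point holds as a mismatch between the stated test and the stated question. This part is structural and rests on no assumed number: a four-bread F cannot distinguish fibre from β-glucan, and section 4 names no comparison that can. Table 1 leaves one fibre-matched comparison, barley versus whole-wheat, and contradicts the equal-fibre description for oat bread.

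The size is illustrative. The plan gives no SD, and the percentages assume shifts in within-subject SD, sphericity and two-sided tests. At n = 16 and 1σ, F is significant in 80% against 91% of trials under the two explanations, and the barley contrast in 5% against 75%.

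This should be fixed, but it does not undermine the design. The plan omits the needed contrast; it does not adopt a wrong decision rule.

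**What to change.** In section 4.2:

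- Name barley minus whole-wheat as the within-participant contrast for any claim of an effect independent of total fibre. Test it at two-sided 0.05 for each primary outcome and report the estimate with a 95% CI. Adjust across outcomes if any one of them can support the claim alone. The primary outcomes must be named for this, because section 4.1 only refers to them in the plural.
- State that the claim will not rest on the omnibus F or on oat versus whole-wheat.
- Keep the ANOVA as the overall test of bread differences. Report the remaining pairs (oat vs whole-wheat, barley vs white, oat vs white, white vs whole-wheat, barley vs oat) with CIs and a multiplicity adjustment such as Holm.

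In sections 2 and 3.1, correct the fibre wording so that it agrees with Table 1 for oat bread.

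Section 4 is written in the past tense. If the data have already been seen, label the contrasts post hoc; the fix then clarifies interpretation but cannot supply prespecified error control.

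The cost is wording and a few contrast statements, with no new data. The downside is power. At a true shift of 1σ the barley contrast has about 75% power with 16 completers and 85% with 20. If two outcomes share the alpha (0.025 each), this falls to 64% and 76%. The shift detectable with 80% power at 0.05 is 1.06σ with 16 and 0.93σ with 20. A non-significant barley contrast would therefore not show absence of an effect and should be read from its CI.
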